Missing Data: Patients who refuse to return for follow-up or who cannot be located and/or do not formally withdraw consent are described as "missing data." Sites will be instructed to continue efforts to contact these patients. See Statistical Plan for more information on how missing data will be handled in the analysis.

Osteolysis: As defined in Exhibit 3: Radiographic Protocol.

Other Interventions: This category includes other surgeries the patient incurs while enrolled in the study that are seemingly unrelated to the implanted device. This would include surgeries such as cholecystectomy, appendectomy, coronary artery bypass surgery, etc.

Revision: A procedure that removes part of the original implant configuration, with or without replacement of the entire component configuration.

Removal: A procedure where the entire original system configuration is removed.

Reoperation: Any surgical procedure that does not include removal or revision, for example, drainage of a hematoma at the surgical site.

Screen Failure: A patient who is either screened but not consented, consented but not randomized or randomized but does not receive the investigational or control device.

Adverse Event (AE): Any event occurring in a study subject that, in the opinion of an M.D. or other qualified and trained medical professional, represents an untoward medical occurrence that differs in either nature, severity, or frequency from a normal post-operative finding. AEs may not have an apparent causal relationship with the device. An AE can therefore be any discrete or ongoing unfavorable and unintended sign (including an abnormal laboratory finding), symptom, or disease temporally associated with the use of a product.

Serious Adverse Event: Any untoward medical occurrence that:

- Results in death
- Is life-threatening
- Requires in-patient hospitalization* or prolongation of existing hospitalization
- Results in persistent or significant disability/incapacity
- Results in congenital anomaly/birth defect

*A planned hospitalization for a pre-existing condition, or a procedure required by the protocol, without a serious deterioration in health is not considered to be a serious adverse event.

Unanticipated Adverse Device Event: any serious adverse event that is or may possibly be related to the device other than those listed in Section C: Risk Analysis or in the institution's approved Informed Consent.

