A significant disability is one that causes substantial disruption to the person's normal life and activity.

The investigator or designee must complete the SAE reporting (SAE100). Then relative to the event, a Revision/Removal Form (RR 100), and/or the Withdrawal Form (WD100) form should be completed. See the Implant Retrieval and Analysis of Removed Implants section below for instructions on how to handle investigational devices that are removed from study subjects.

DISCONTINUATIONS AND REVISIONS (SUBJECT WITHDRAWAL)

It is recognized that the subject's participation in this trial is entirely voluntary, and that she/he may refuse to participate and may withdraw from participation at any time without jeopardy to any future medical care. Device Revision or Removal is also considered a withdrawal event when all components are removed, or if only the humeral stem is removed. No additional study follow-up is necessary. In the event that a patient receives a partial revision (not all components/humeral stem), a revision/removal form should be completed, but the patient should still be followed per protocol. Do not complete a withdrawal form for these patients. *Enrollment for this study is defined as receipt of either a control or an investigational device.*

Therefore:

- Subjects withdrawn from the study after receipt of either the control or investigational device will NOT be replaced.
- Randomized patients who do not ultimately receive the control or investigational device:
 - 1. *WILL* be replaced, but
 - 2. Randomization assignment will not be re-used
- *All* subject withdrawals must be documented on the Withdrawal Form (WD100).

- Includes randomized patients who do not ultimately receive the control or investigational device configurations.
- If withdrawal is due to device removal or revision, the SAE 100 form must be completed. The Revision/Removal form (RR 100) should be completed in all cases including device removal details, if known.

Copies of all Case Report Forms are included in Exhibit 4.

CONTROL OF INVESTIGATIONAL DEVICE

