The three co-primary endpoints for this study are:

- a. ASES score at 22+ Months
- b. No unanticipated device-related adverse event, and no fracture, perforation of the bone or joint dislocation, and no fracture, perforation or dissociation of the device, and no revision or removal of any component, and
- c. Radiographic Success, as defined by:
 - a. Subsidence of the humeral component < 5 mm, and
 - b. Migration of the humeral component < 5mm, and
 - c. No progressive lucency around the humeral component >2mm in two or more contiguous zones
 - d. Migration of the glenoid component <5 mm, and
 - e. No progressive lucency >2mm around the entire glenoid component

SECONDARY ENDPOINTS

The data collected will also be analyzed for the following secondary endpoints:

- 1. American Shoulder and Elbow Surgeon's Score (ASES) at all time points
- 2. Single Assessment Numeric Evaluation (SANE) Score at all time points
- 3. Constant Score at all time points, except 6 weeks (adjusted for age and gender)
- 4. Radiographic assessment of radiolucencies and subsidence
- 5. Overall adverse events including removal/revision and other serious adverse events

The safety of the system will be monitored by recording adverse events including serious adverse events not considered UADEs throughout the follow-up period. Types of events to be collected include but are not limited to:

- Device removal or revisions
- Unanticipated adverse device events
- Systemic adverse events
- Local adverse events
- Reoperations and Other Interventions

Study participants will only be considered discontinued/withdrawn for the following reasons:

- Death
- Withdrawal of consent (written)
- Revision/Removal

Information from any patient who fails to return for multiple, consecutive, scheduled follow-up visits for any reason other than the criteria listed above will be identified as Missing Data.

ANTICIPATED CHANGES

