Subjects who have been randomized to the Investigational or Control group in this study comprise the All Enrolled population. The co-primary endpoints will be analyzed for the All Enrolled population and the results will be compared to the primary analyses performed on the Analysis population to determine whether the results of this analysis are consistent for both populations. For patients in the All Enrolled Population who are missing data necessary for the determination of any of the co-primary endpoints at 22+ months, data will be imputed as described below in the section "Sensitivity Analyses."

ANALYSIS POPULATION

Subjects who have been randomized to the Investigational or Control group in this study and who have complete data for a primary endpoint collected per the protocol at 22+ months or who have had a revision or removal at or before 26 Months will be included in the Analysis Population. This is the population that will be used in the primary study analysis and determination of study success. Those subjects who are missing their primary endpoint at 22+ months will be included as part of the All Enrolled population described above. Subjects with protocol deviations will be analyzed on an individual basis to determine if they will be included in the Analysis Population.

MISSING DATA AND SENSITIVITY ANALYSES

Data will be considered "missing" for a given primary endpoint if this endpoint cannot be calculated or is not available for a subject in the All Enrolled population. If the subject has had a

device failure at any point on or prior to their 22+ month outcome, they will *not* be considered as missing data for the Absence of Revision/Removal/UADE endpoint, as this endpoint is cumulative. A subject who has had a revision or removal prior to two years will be considered a radiographic failure at the 22+ month time point for purposes of the primary analysis. When possible (i.e. the subject is seen by a study investigator in a non-emergency situation and collection of the data will not cause undue burden), ASES scores will be collected for these cases before the revision is performed in order to prevent these patients from missing knee scores in the primary efficacy analyses.

Sensitivity analyses will examine the sensitivity of the results to missing values of the primary outcomes using the following analyses:

Outcome Type	Analysis Description	
Binary	Tipping Point Analysis: Missing observations are replaced with	

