Subject covariates in the proposed statistical modeling below include treatment group, age at time of surgery, gender, BMI, primary diagnosis, and preoperative ASES score. Others may be added if other covariates potentially affecting the outcome become apparent. To determine the effect of these covariates on the primary endpoints, separate regression models will be used. In the regression models, the dependent variable will be the primary study endpoint; thus a logistic regression model will be needed for the binary study endpoints. The baseline and demographic variables listed above will be independent variables. A graphical examination of the residuals will be performed to assess the model assumptions. To determine whether a covariate has an effect on the primary study outcome, a Type 3 analysis of effects based on the Wald Chi-square test will be conducted.

In addition, the time to revision will be calculated for each subject in the investigative and control groups. For those individuals that do not experience a revision, their outcome will be classified as censored. Failure-free curves will summarize and illustrate the proportion of endpoint-free subjects for the Investigational and Control groups over the course of the study. The Kaplan-Meier product-limit method will be used to construct the endpoint-free curves for the Investigational and Control groups.

Also, a proportional hazards regression model will be fit to model the time-to-revision and censored data¹⁰. The principle time-to-revision model will include an independent variable for treatment group as well as baseline covariates that may have an effect on survival. The proportional hazards assumption will be assessed graphically and analytically. Once an adequate model has been fit, for the treatment effect and its standard error parameters will be

¹⁴ Exploratory Analyses described will be carried out if possible, depending on the data. If empty cells exist or models do not converge, these analyses will not be performed.

estimated using partial likelihood. If there are a small number of tied event times, exact methods will be used to compute the likelihood; alternatively, Efron's approximation will be used¹¹.

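### As worded, the exploratory time-to-revision analysis censors shoulders whose entire implant is removed, although its curves are labelled failure-free

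*Combined protocol and SAP*

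**What the plan says.** The glossary (protocol, Study Definitions and Glossary of Abbreviations) has two entries. Revision is "A procedure that removes part of the original implant configuration, with or without replacement of the entire component configuration". Removal is "A procedure where the entire original system configuration is removed".

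The SAP, under Exploratory Analyses, computes a time to revision for each subject and adds: "For those individuals that do not experience a revision, their outcome will be classified as censored". The output is described as follows: "Failure-free curves will summarize and illustrate the proportion of endpoint-free subjects", by arm and by the Kaplan-Meier method. A proportional hazards model is fitted to the same data. Removal is not mentioned in that text.

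Other outcome rules name both events. The co-primary safety endpoint requires "no revision or removal of any component" among its conditions, and the corresponding hypothesis is titled Absence of Revision/Removal/UADE. Under Missing Data and Sensitivity Analyses: "A subject who has had a revision or removal prior to two years will be considered a radiographic failure". The Analysis Population and the adverse event comparison under Safety Evaluations also refer to both.

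On follow-up, the section Discontinuations and Revisions says: "Device Revision or Removal is also considered a withdrawal event when all components are removed, or if only the humeral stem is removed". No further study follow-up is required after that.

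**The concern.** A survival analysis is defined by its event and its censoring rule. Here the event is the narrower of two defined terms, and everyone without it is censored. Read with the glossary, complete loss of the implant is therefore handled as a non-failure. Complete removal also ends study follow-up, so the censoring time is the moment of failure. That is informative censoring, and nothing in the text prevents it.

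At stake is a descriptive result. The failure-free proportion would be too high in any arm where a complete removal occurs. Two analysts working from the same data and the same SAP could also draw different curves, depending on how they read one word.

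**Working it through.** **The plan's own figures.** No figure is stated for the time-to-revision analysis, so none is in dispute. The nearby figures reproduce:

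- The cited revision rate is 1/49 = 2.04%, stated as 2.0%.
- The Absence of Revision/Removal/UADE calculation (95% in both arms, margin 0.10, one-sided 5%, 90% power) gives 82 per arm, and 82/0.85 = 96.5, rounded up to 97.
- The radiographic calculation (93% in both arms, otherwise the same) gives 112 per arm, and 112/0.85 = 131.8, rounded up to 132. This is the arm size used below.

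**The definitions applied.**

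1. A shoulder whose whole system is taken out meets the glossary entry for removal.
2. The entry for revision requires that part of the configuration be taken out.
3. The time-to-revision rule makes revision the event and censors everyone else.
4. So, on the glossary's terms, the shoulder in step 1 is censored. In the co-primary safety endpoint and the radiographic failure rule the same shoulder is a failure.

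**Size per removal.** The Kaplan-Meier estimate is the product of (1 − 1/number at risk) over the events. With 132 per arm and no other censoring, leaving out one removal raises the estimate by about 1/132 = 0.76 points. It is slightly less when removals come before the other events: with 2 removals then 3 revisions, (127/130 − 127/132)/2 = 0.74 points each. If attrition had already reduced the number at risk to 112 (an assumption), one step would be about 1/112 = 0.89 points.

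**Illustration.** The counts are assumed, because the documents give none. The last column gives the estimate with the removals occurring first and then last.

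| Losses in an arm | Of these, complete removals | All losses counted | Removals censored |
|---|---|---|---|
| 3 | 1 | 129/132 = 97.7% | 129/131 = 98.5%; 130/132 = 98.5% |
| 3 | 3 | 97.7% | 100% |
| 5 | 2 | 127/132 = 96.2% | 127/130 = 97.7%; 129/132 = 97.7% |
| 5 | 3 | 96.2% | 127/129 = 98.4%; 130/132 = 98.5% |
| 5 | 5 | 96.2% | 100% |
| 8 | 3 | 124/132 = 93.9% | 124/129 = 96.1%; 127/132 = 96.2% |
| 8 | 8 | 93.9% | 100% |

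**The case against.** The strongest reply is that the documents do not keep to their own glossary, so the harmful reading may not be the intended one.

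- Discontinuations and Revisions needs the expression partial revision for cases where some components stay. That would be redundant if revision always meant partial.
- Study Groups and Treatments lets blinding end when a patient is revised, on the ground that data collection stops. That fits the cases that count as withdrawals, which include complete removal.
- Missing Data and Sensitivity Analyses introduces revision or removal cases and then speaks only of the revision when saying when ASES should be collected.
- Subject Accounting has a line for revisions and none for removals.
- The glossary entry for revision is itself not clean: its closing clause could let a full exchange count as a revision.

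All of this stands. It shows that the sponsor may have meant any component loss. It does not show that the time-to-revision text says so, and a defined term is what a programmer will apply.

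The second reply is that no decision depends on this analysis. That also stands. Under Significance Levels, exploratory results carry no claim of significance. Removals are counted where success is decided and in the safety comparison. The proportional hazards model would have few events to work with, and the footnote to Exploratory Analyses allows it to be dropped.

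**Conclusion.** The point holds as a small error in the wording. Under the protocol's own definitions the stated rule overstates failure-free survival by about 0.76 points for each complete removal in an arm of 132, assuming little other censoring. Severity is minor: the analysis is exploratory, and the co-primary tests and study success are unaffected.

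Four stronger readings are tempting, and the documents do not support them.

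- **That a true 2% failure rate would appear as about 1%.** The 2% is a reported revision rate from one case in 49. No share of removals is given, so halving it is a guess.
- **That the comparison favours one device.** This requires the share of removals to differ by arm. Such a case can be constructed: with 6 investigational losses, 4 of them removals occurring first, and 3 control revisions, counting all gives 126/132 = 95.5% against 129/132 = 97.7%, while the literal rule gives 126/128 = 98.4% against 97.7%. These counts are invented. The risk section mentions a possible increase in loosening or migration with the stemless design, but says nothing about complete removal as opposed to partial revision.
- **That the curve would contradict the revision and removal counts.** On the strict reading it would show a narrower event under a misleading label.
- **That removed shoulders will certainly be reported as survivors.** That depends on how the loosely used term is applied.

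**What to change.** In Exploratory Analyses, define the event for both the Kaplan-Meier curves and the proportional hazards model as the first revision or removal of any component. This is the revision and removal element of the co-primary safety endpoint only, without its fracture, perforation, dislocation, dissociation and UADE elements. State that a withdrawal caused by device removal is an event at the date of the procedure, and that all other subjects are censored at death, withdrawal of consent or last contact. Rename the analysis time to first revision or removal.

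The cost is a sentence or two in the SAP. The Revision/Removal form (RR100) already collects the data, and the design, sample size and study conduct do not change.

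### Footnote 14 cancels exploratory analyses when cells are empty or a model fails to converge and names no fallback, so the adjusted time-to-revision estimate can be lost because of the outcome data

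*Combined protocol and SAP*

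**What the plan says.** The rule is a footnote to the heading Exploratory Analyses, under Efficacy Evaluations in the Statistical Analysis Plan. It reads: "Exploratory Analyses described will be carried out if possible, depending on the data", followed by "If empty cells exist or models do not converge, these analyses will not be performed". It does not say which cells count, whether one failure cancels one model or all of them, or what is reported instead.

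The analyses under that heading include:

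- Regression of each primary endpoint on "treatment group, age at time of surgery, gender, BMI, primary diagnosis, and preoperative ASES score", with more covariates possible. For the two binary endpoints, "a logistic regression model will be needed for the binary study endpoints". To judge covariates, "a Type 3 analysis of effects based on the Wald Chi-square test will be conducted".
- Kaplan-Meier curves of time to revision.
- A Cox model: "a proportional hazards regression model will be fit to model the time-to-revision and censored data". On its content: "The principle time-to-revision model will include an independent variable for treatment group as well as baseline covariates". The covariates are not listed.
- t-tests of ASES change by radiographic finding, and a Fisher's exact test of reoperation rates.

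Revisions are also handled outside the footnote. The safety co-primary endpoint requires "no revision or removal of any component", among other conditions (Co-Primary Endpoints), and is tested by a one-sided Wald bound (Efficacy Evaluations, Primary Endpoint). Revisions and removals are compared by arm under Safety Evaluations and counted under Subject Accounting. The Significance Levels section says that exploratory results carry no claim of significance.

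**The concern.** Revisions are expected to be few. If one arm has none, ordinary partial likelihood has no finite maximum for the treatment effect, and the plan's response is to omit the analysis. Whether a pre-specified adjusted estimate is reported then depends on how the outcomes happened to fall, and readers would see neither the estimate nor a planned substitute.

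Two features add to this. Read literally, the footnote also removes the Kaplan-Meier curves and the reoperation test, neither of which needs a model to converge. And where a sparse logistic model does converge, Type 3 Wald tests on two or three events per term are a weak guide to whether a covariate matters.

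At stake is the completeness of the exploratory evidence on device survival, not the study's success decision.

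**Working it through.** **Inputs from the plan.** Enrolment is 132 per arm, 264 in total, with 112 per arm evaluable (Number of Procedures; Sample Size Calculation). The revision rate is 2.0%, from one revision in 49 patients. Safety-endpoint failure is 5% (2% + 2% + 1%) and radiographic failure is 7% (Sample Size Calculation). The regression lists six variables. **Assumptions added here:** a 1% revision rate as a lower scenario, a 6% investigational rate as a harm scenario, and independent shoulders.

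**1. The plan's sample sizes.** n per arm = (1.645 + 1.282)² × 2p(1 − p) / 0.10².
- p = 0.93: 8.57 × 0.1302 / 0.01 = 111.5, so 112; 112 / 0.85 = 131.8, so 132.
- p = 0.95: 8.57 × 0.095 / 0.01 = 81.4, so 82; 82 / 0.85 = 96.5, so 97.

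Both stated figures are reproduced with this unpooled-variance formula.

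**2. Events available.**
- Revisions: 0.02 × 264 = 5.3.
- Safety-endpoint failures: 0.05 × 224 = 11.2; 11.2 / 6 = 1.9 per term.
- Radiographic failures: 0.07 × 224 = 15.7; 15.7 / 6 = 2.6 per term.

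**3. Chance of an arm with no events.** P(one given arm) = (1 − p)^n. With equal rates, P(at least one arm) = 1 − [1 − (1 − p)^n]².

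| Outcome | Rate, both arms | n per arm | One given arm | At least one arm |
|---|---|---|---|---|
| Revision | 2% | 132 | 6.9% | 13.4% |
| Revision | 2% | 112 | 10.4% | 19.7% |
| Revision | 1% (assumed) | 132 | 26.5% | 46.0% |
| Safety composite | 5% | 132 | 0.11% | 0.2% |
| Safety composite | 5% | 112 | 0.32% | 0.6% |
| Radiographic | 7% | 112 | 0.03% | 0.06% |

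**4. Is the trigger specific to harm?** With control at 2% and the investigational arm at an assumed 6%, 132 per arm: 0.98^132 + 0.94^132 − their product = 0.0695 + 0.0003 − 0.00002 = 7.0%. That is lower than the 13.4% under equal 2% rates.

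**5. The case 0/132 against 6/132.**
- Two-sided Fisher p = 2 × C(132,6) / C(264,6) = 0.029.
- The likelihood-ratio chi-square named under Safety Evaluations gives p = 0.004.
- If these are the only safety failures, the plan's Wald bound is 6/132 + 1.645 × √(0.0455 × 0.9545 / 132) = 0.0455 + 0.0298 = 0.075, inside the 0.10 margin. At 0 against 9 it is 0.104, and non-inferiority fails.
- A treatment-only logistic model, standing in for the Cox model, has no finite maximum-likelihood estimate. Firth's method gives an odds ratio of 13.6 (95% profile interval 1.58 to 1783), p = 0.012.

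**6. Is non-convergence a usable switch?** Ordinary maximum likelihood was run on three tables with no control events. With 3 investigational events the software flagged non-convergence. With 6 it reported convergence with a standard error of about 3 × 10⁷. With 8 it stopped on a singular matrix. The same defect produced three different signals, so the footnote's condition does not define one clear action.

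**The case against.** A reader might infer that reporting of revision harm itself depends on the result: that it disappears when the arms differ most and stays when they look alike. The documents do not support that, for three reasons.

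- The unadjusted comparison of revisions and removals and the co-primary safety test lie outside the footnote and carry no cell-count condition. At 0 against 6 both still run.
- The trigger is few events. An arm without revisions is more likely under equal 2% rates (13.4%) than under an assumed 6% investigational rate (7.0%). Sparse covariate levels could also set it off.
- The logistic models use composite endpoints. All revisions falling in one arm does not empty the treatment cell unless every other failure falls there too, and the chance of an arm with no failures is 0.6% or less at the planned rates.

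It can also be said that these analyses support no claim of significance, that the Wald tests decide nothing about study success, and that Firth's method is one reasonable choice among several. All of this stands, and it keeps the point minor. It does not answer the narrower one: the footnote names no fallback, does not define its own trigger, and extends to analyses that do not need it.

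**Conclusion.** The point holds as a cheap improvement. A pre-specified exploratory estimate, chiefly the adjusted time-to-revision effect, can be dropped because of the outcome data. From an empty treatment cell alone, the chance is 13.4% at the plan's 2% rate with 132 per arm, 19.7% at 112 per arm, and 46% at an assumed 1% rate. The logistic models are unlikely to be lost this way, but their Type 3 Wald tests rest on about 1.9 and 2.6 events per term.

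These figures assume independent shoulders and equal rates in the arms. The 2% rests on a single revision in 49 patients, and longer follow-up would add events. The low figures for the safety composite use the wide definition under Co-Primary Endpoints, on which the sample size is built. The hypothesis section describes that endpoint only as revision, removal or UADE. Read that way, failures would be rarer and an empty arm correspondingly more likely. No estimate is made here for empty covariate cells, because the plan gives no covariate distributions.

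**What to change.** Replace footnote 14 with a rule along these lines:

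- A model that is separated or does not converge is refitted with Firth's penalised likelihood, with profile-likelihood intervals and penalised likelihood-ratio tests in place of Wald tests.
- The rule applies only to the model that fails, and each failure is reported.
- The time-to-revision model contains treatment and at most one named covariate.
- The Kaplan-Meier curves, the reoperation Fisher test and an exact or log-rank comparison of revisions are always reported.

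The cost is a model option and a few lines of SAP text. The downside is slightly shrunken estimates and wide intervals, as the upper limit of 1783 in the example shows. Sample size, data collection and the primary tests are unchanged.
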